15.6 Exploratory Objectives

Exploratory objectives include: (1) estimation of overall survival and progression-free survival, (2) examination of the effect of ELISpot results on subsequent OS or PFS, (3) estimation of the radiographic response rate, (4) determination of whether tumors are IDH1 negative at surgery, (5) characterization of immunologic cell infiltrate, (6) determination of whether IDH R132H can be detected in plasma and whether the study treatment will affect the levels detected, (7) determination of whether IDH 2HG can be detected in plasma and whether the study treatment will affect levels detected, (8) genomic and proteomic analyses, and (9) an assessment of metabolic imaging.

 The Kaplan-Meier estimator will describe the survival, PFS from vaccine #1, and PFS post-resection of patients treated with PEP_{IDH1M} vaccine. Survival is defined as the time between first vaccine and death, or last follow-up if the patient remains alive. PFS from vaccine #1 is defined as the time between vaccine #1 and initial progression or death, or date of last follow-up if the patient remains alive without disease progression. PFS post-resection is similarly defined but starting at resection. The proportion of patients alive without progression 6 months after resection will be estimated from the

Cox proportional hazards model will be used to explore the association between ELISpot outcome and

- 2. Cox proportional nazards model will be used to explore the association between ELISpot outcome and subsequent OS or PFS. The radiographic response rate (complete response + partial response) will be estimated with a 95% confidence interval.
- 3. The proportion of tumors that are IDH1 negative at the time of surgery will be estimated, with a 95% confidence interval.
- 4. Means and standard deviations, as well as quantiles, will be used to describe the distribution of immunologic cell infiltrates found in tumors at the time of surgery.
- 5. Descriptive statistics will be used to describe the changes over time in the level of IDH R132H as measured from tumor-specific circulating DNA.
- 6. In a similar manner, changes over time in levels of the 2-HG metabolite as measured by mass spectrometry will be described.
- 7. Genomic and proteomic analyses of the pre-treatment pathologic specimen and the post-vaccination surgical sample will be conducted. Changes in genetic alterations, differential protein expressions and PTMs will be described. If statistical tests are conducted, appropriate adjustment for multiplicity will be considered.
- Measures of metabolism in IDH1+ gliomas will be assessed at several time points. Paired comparison (e.g. paired t-tests) will be used to assess whether same-day measures on a patient are the same. Assuming repeatability, changes over time in levels of metabolism will be described.

Additional exploratory analyses may be conducted. Among these additional exploratory analyses will be an examination of the relationship among changes in metabolism, genomic expression, 2-HG metabolite, and pathologic expression of IDH.

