9 INVESTIGATIONAL PLAN

9.1 Study Design

Subjects with radiographic and/or clinical progressive and resectable Grade II glioma with expression of IDH1^{R132H} from the primary tumor (initial diagnosis) will be enrolled after signing informed consent. After consent has been signed, **all** subjects will undergo standard of care vaccination with 0.5 mL of Td (tetanus and diphtheria toxoids adsorbed) intramuscularly (I.M.) into the deltoid muscle to ensure adequate immunity to the tetanus antigen. The tetanus vaccine will be obtained through Duke ICS Pharmacy.

Eligible subjects will undergo a 1-2 hour leukapheresis for immune monitoring. Within 48 hours of leukapheresis, subjects will receive a vaccine site pre-conditioning as a single dose of Td toxoid (1 flocculation unit, Lf, in a total volume of 0.4 mLs saline). This will be administered one day prior to receiving PEP_{IDH1M} vaccine intradermally (i.d.) to the RIGHT groin area (as described below). The peptide vaccine is administered in the groin area approximately 10 cm below the inguinal ligament as vaccine # 1. Subsequent vaccines will be given on day 15 ±3 days (vaccine #2) and day 29 ±3 days (vaccine #3). These injections will occur without TMZ. Each injection of the peptide vaccine will be given half on the right groin and half on the left groin.

Seven to 12 days after the 3rd vaccine, subjects will undergo surgical resection of tumor, which is part of the SOC for these subjects. If possible, the provider will take a photo of the injection site at the pre-op appointment seven to twelve days after the 3rd vaccine to document the subject's reaction to the vaccine. Tumor samples from the surgical resection will be evaluated as outlined in the Exploratory Objectives.

Based on tissue obtained at surgical resection, subjects with stable histologic grade at recurrence will then be treated with vaccine and adjuvant TMZ at a targeted dose of 50-100mg/m²/d for 21 days every 28 days for up to 12 cycles (please see Section 18.5 in the Appendices for TMZ). During monthly cycles of TMZ, subjects will receive the vaccine on day 22 (+ 2 days) for a maximum of 15 total vaccines (which includes the first 3 bi-weekly vaccines). Patients that have transitioned to a higher Grade brain tumor will receive TMZ and radiation therapy per standard of care and monthly vaccines.

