Subsequent vaccines will be given on day 15 \pm 3 days (vaccine #2) and day 29 \pm 3 days (vaccine #3). Seven to 12 days after the 3rd vaccine, subjects will undergo surgical resection which is part of the SOC for these subjects. Patients with re-confirmed Grade II will be treated with adjuvant TMZ and vaccine. Patients that have transitioned to a higher Grade brain tumor will receive TMZ and radiation therapy per standard of care and monthly vaccines. For higher grade gliomas undergoing RT, vaccine #4 will be given during SOC clinic visit prior to initiating RT, and vaccine #5 will be given 4 weeks later (\pm 1 week) during RT. Vaccine #6 will be given at the end of RT during the SOC clinic visit to review MRI and begin post-RT TMZ, if MRI stable. Then, subjects in this treatment group will receive vaccines monthly on day 22 (+2 days) with post-RT cycles of TMZ to a maximum of 15 vaccines.

If possible, the provider will take a photo of the injection site at the pre-op appointment seven to twelve days after vaccine #3 to document the subject's reaction to the vaccine. The provider may take additional pictures of the injection site at other clinic visits at the discretion of the treating physician or Principal Investigator. There will be no identifiers on the photographs. The photographs will be taken by the subject's provider and may be uploaded to their electronic medical record or kept in a separate electronic or paper research file. The photographs will be uploaded to the electronic medical record by using electronic applications called Haiku for iPhones or Cantu for iPads. These applications allow for the photograph to be uploaded directly to the electronic medical record without the photographs being stored on the device taking the picture. A ruler will be included in the photo to allow measurement of the size of the injection site reaction.

To demonstrate quantitative repeatable measures of 2HG change in IDH1+ gliomas, patients will be scanned on the CAMRD MR scanner using a an MRS protocol. We will acquire MRS data at up to 5 time points: baseline (after consent and before PEP_{IDH1M} vaccine #1) and up to 4 times prior to surgery (please refer to Section 9.5 for more detail).

IDH1 R132H biomarker component of the protocol and immune monitoring:

a) Study of tumor-specific circulating nucleic acid from plasma of patients with gliomas with IDH1 R132H:

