15.1 Analysis Sets

Subject to the availability of data, all patients who receive any protocol treatment will be included in analyses addressing secondary objectives. Statistical analyses for the primary objective will exclude patients who terminate protocol treatment prematurely (i.e. less than 6 vaccinations) without an unacceptable toxicity.

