Any patient who discontinues vaccination prior to the receipt of 6 vaccines will not be evaluable for the primary endpoint, unless the patient experienced an unacceptable toxicity. Per Section 12.6.3, these patients will be replaced. Patients who are determined at the time of surgery to have transformed from

Grade II to a higher grade will receive TMZ and radiation therapy per standard of care and monthly vaccines and will be included in the final analysis of the primary objective.

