18.5 Temozolomide Therapy

18.5.1 Concurrent TMZ and RT

For subjects who progress to Grade 3 at the time of surgery, TMZ should be administered concomitant with standard external beam RT under the direction of the study Neuro-Oncologists (listed on title page), or their designees, respectively, at Duke University or another institution at the standard dose per discretion of the treating neuro-oncologist. During standard RT, subjects will receive 75mg/m²/day TMZ for 42 days (6 weeks).

Per the new NCI Temozolomide (NSC 362856) Action Letter:

- Liver function tests (or CMP) should be performed:
 - prior to treatment initiation. If abnormal, the decision to initiate temozolomide treatment should carefully consider the benefits and risks for the individual patient; after each treatment cycle.
- For patients on a 42 day treatment cycle, liver function tests should be repeated midway during this cycle;
- For patients with significant liver function abnormalities the benefits and risks of continuing treatment should be carefully considered.

If any interruption occurs or dose reduction is required, TMZ may be resumed when re-treatment criteria are met as outlined in Table 5 and Table 6.

Dose reduction or alteration during this period due to toxicity is standardly performed as outlined in Table 5.

Toxicity	TMZ Interruption ^a	TMZ Discontinuation		
Absolute Neutrophil Count	> 0.5 and <1.0 x 10 ⁹ /L	<0.5 x 10 ⁹ /L		
Platelet Count	> 10 and <100 x 10 ⁹ /L	<10 x 10 ⁹ /L		
Common toxicity criteria (CTC ²) Non- hematological Toxicity (except for alopecia, nausea, vomiting)	CTC Grade 2	CTC Grade 3 or 4		
a: Treatment with concomitant TMZ can be continued when all of the following conditions are met: absolute neutrophil count \geq 1.0 x 10 ⁹ /L; platelet count \geq 100 x 10 ⁹ /L; CTC non- hematological toxicity \leq Grade 1 (except for alopecia, nausea, vomiting).				

The dose may be modified as outlined in Table 6 at the discretion of the treating oncologist.

Table 6. Dose Modifications of Temozolomide during Radiation Therapy

Dose at Toxicity	Modified Dose
75 mg/m2 (during XRT)	60 mg/m2
60 mg/m2 (during XRT)	50 mg/m2

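### Section 15.6 relates ELISpot to PFS and OS with no account of grade at surgery, although grade decides both the post-surgery treatment and the conditions of the vaccine #6 ELISpot sample

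*Combined protocol and SAP*

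**What the plan says.** On outcome, Section 15.6 states: "The Kaplan-Meier estimator will describe the survival, PFS from vaccine #1, and PFS post-resection of patients treated with PEP_{IDH1M} vaccine". On immune response: "Cox proportional hazards model will be used to explore the association between ELISpot outcome" and later OS or PFS. Neither item mentions grade at surgery. Section 15.1 says "all patients who receive any protocol treatment will be included in analyses addressing secondary objectives" and defines no separate set for the exploratory ones. Section 15.4.2 keeps upgraded patients in the primary analysis ("vaccines and will be included in the final analysis of the primary objective"), also without separate handling.

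Treatment after surgery depends on grade. In Section 9.1, "subjects with stable histologic grade at recurrence will then be treated with vaccine and adjuvant TMZ". In Section 12, "Patients that have transitioned to a higher Grade brain tumor will receive TMZ and radiation therapy per standard of care and monthly vaccines".

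Section 15.5 plans two ELISpot readings: one before surgery, after three vaccines, and one after three further vaccines. By Section 9.1 and the Table 2 footnotes, vaccine #6 is given on day 22 of a TMZ cycle in confirmed Grade II patients and at the end of RT in upgraded patients.

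**The concern.** Grade at surgery could confound the link between the post-surgery ELISpot and outcome. It decides the treatment that follows, it may carry prognostic information, and it fixes the circumstances in which the second sample is drawn. A Cox model that leaves grade out can then credit the immune response with a difference that belongs to grade or to treatment.

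This matters because Section 9.3 intends the immune-correlate analyses to supply the starting data for powering later studies. A spurious hazard ratio would feed directly into those calculations.

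**Working it through.** **The plan's own figures.** The documents give no event count, power, hazard ratio or upgrade rate for the Cox model or the curves, so there is nothing to reproduce there. The nearest stated figure is in Section 15.5: 80% power for 4.17 SFC with 20 patients. It reproduces. With SD √(3.6² + 6.3²) = 7.26, a one-sided 5% paired t-test has power 0.797; a two-sided test with SD 6.3 gives about 0.80. It does not bear on the present point.

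**Conditions at the vaccine #6 sample.**

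| | Confirmed Grade II | Upgraded |
|---|---|---|
| Treatment after surgery | 21-day TMZ cycles starting at 50 mg/m²/day (18.5.2) | RT with TMZ 75 mg/m²/day for 42 days (18.5.1), then 21-day cycles |
| Vaccines #4-6 | Day 22 of cycles 1-3 | Before, during and at the end of RT |

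The pre-surgery reading comes before this divergence, so the difference in treatment cannot affect it. There, grade could confound only through tumour biology.

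**Are the two links supported?**
- *Grade and prognosis.* Section 7.1 sets grades II and III together against primary GBM and gives no II-versus-III figure. A prognostic effect is plausible but not quantified.
- *Grade and ELISpot.* Section 7.3.1 reports stronger responses with the higher TMZ dose, and Section 9.2 argues that lymphopenia may enhance responses. A difference between the groups is plausible, but its sign is open.

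**Simulation.** All inputs are assumptions:
- true ELISpot effect zero;
- 30% or 50% upgraded;
- hazard ratio for upgraded versus Grade II of 2 or 4;
- ELISpot lower in upgraded patients by 0.5 or 1 within-grade SD;
- Grade II median PFS 36 months, exponential times, 60 months of follow-up;
- 6,000 runs per setting, two-sided 5% Cox score test.

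| Setting | Unstratified: rejection, median HR per SD | Stratified: rejection, median HR per SD |
|---|---|---|
| n=20, 30%, HR 2, 0.5 SD | 6.3%, 0.93 | 5.7%, 1.00 |
| n=20, 50%, HR 4, 1 SD | 17.6%, 0.77 | 5.9%, 1.00 |
| n=28, 30%, HR 2, 0.5 SD | 6.8%, 0.93 | 5.6%, 1.00 |
| n=28, 50%, HR 4, 1 SD | 24.0%, 0.77 | 5.5%, 1.00 |

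Over all settings with both links present, the stratified test rejects 5.1% to 6.3%. With HR 1 or no ELISpot shift, the unstratified test stays at 5.0% to 5.9%. Monte Carlo error is about 0.3 points near 5% and 0.5 near 20%. Reversing the sign of the shift leaves the rejection rates unchanged and inverts the hazard ratios: 1/0.93 = 1.08 and 1/0.77 = 1.30.

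**Curves.** With S(t) = (1−p)·2^(−t/36) + p·2^(−HR·t/36), the pooled median is 28.9 months (p = 0.3, HR 2) or 16.7 months (p = 0.5, HR 4). The group medians are 36 months for Grade II and 36/HR = 18 or 9 months for upgraded.

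**Upgrade as a PFS event.** Vaccine #3 falls on day 29 ± 3 and surgery 7-12 days later, so between day 26 + 7 = 33 and day 32 + 12 = 44 from vaccine #1, well before the six-month endpoint in Table 1. Under the same assumptions, six-month PFS from vaccine #1 is:
- 0.7 × 0.891 + 0.3 × 0.794 = 0.862 if an upgrade is not an event, against 0.7 × 0.891 = 0.62 if it is (30% upgraded, HR 2);
- 0.5 × 0.891 + 0.5 × 0.630 = 0.760 against 0.5 × 0.891 = 0.45 (50% upgraded, HR 4).

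**The case against.** The strongest reply is that these are exploratory analyses in 20 to 28 patients. Section 9.3 says the study is not meant to be definitive on immune correlates, and Section 15.6 leaves room for further analyses. Power is low in any case: for a binary ELISpot split 1:1 and HR 0.5, Φ(½√D·ln 2 − 1.96) gives 25% at D = 14 events and 34% at D = 20. Section 15.6 is also silent on covariates; it does not rule them out. All of this stands and limits the weight of the point. It does not close the gap, because the general allowance for further analyses commits to nothing on grade.

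Four stronger readings are tempting, and the documents do not support them.

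- *A reader might infer that Section 7.1 shows upgraded patients do worse, and that chemoradiation lowers their ELISpot counts.* Section 7.1 does not compare Grade II with Grade III, and Sections 7.3.1 and 9.2 leave the direction of any ELISpot shift open. The bias could equally make a strong response look harmful.
- *A reader might infer that the pooled curves are invalid.* They validly describe the cohort enrolled, which is progressive Grade II at entry. They are only uninformative about either grade group.
- *A reader might infer that every curve should be split by grade.* Grade is known only at resection. Splitting curves that start at vaccine #1 would classify patients by later information, and those who never reach surgery (a withdrawal reason in 12.6.1) would have no stratum.
- *A reader might infer from Section 18.5.1 ("For subjects who progress to Grade 3 at the time of surgery") that every upgrade is a PFS event.* Section 12.7.4 defines progression by RANO imaging and clinical criteria. Section 12.6.1 refers to progression after post-operative or post-RT immunotherapy has begun. Section 12.2 keeps upgraded patients on treatment. What remains is a wording conflict, because Section 9.3 asks for histological documentation of progression and 15.6 does not say how an upgrade is treated.

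**Conclusion.** The point holds as a cheap improvement to exploratory analyses. Section 15.6 takes no account of grade at surgery, and the exposure is greatest for the vaccine #6 ELISpot. If grade is both prognostic and related to that reading, the unstratified Cox test of a null effect rejects about 6-18% (n=20) or 7-24% (n=28) instead of 5%, with a spurious hazard ratio per SD of 0.93 to 0.77, or the reciprocal if the shift runs the other way. Stratifying returns rejection to about 5-6%. These sizes rest wholly on assumed upgrade rates, hazard ratios and ELISpot shifts; if either link is missing, the inflation disappears. The primary safety conclusion does not change.

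**What to change.** In Section 15.6:

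1. For the post-surgery ELISpot, report a Cox model stratified by grade at surgery (confirmed II versus higher), with time counted from that sample, beside the unstratified model.
2. Show PFS post-resection, and OS counted from resection, by grade beside the pooled curves. Keep the curves from vaccine #1 pooled.
3. Add one sentence that reconciles 15.6, 9.3 and 18.5 on whether an upgrade found at the study resection counts as initial progression, consistent with the RANO definition in 12.7.4.

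The cost is SAP wording, since grade is already reconfirmed at surgery. The downside is small strata (6 to 10 upgraded patients of 20 at 30-50%) and some loss of precision. As a rough guide, the variance factor 1 + d²p(1−p) runs from 1.05 (d = 0.5, p = 0.3) to 1.25 (d = 1, p = 0.5). Grade is also read after three vaccines, so stratifying on it could remove part of a real vaccine effect. The stratified result is therefore a companion to the unadjusted one and does not replace it.

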Exploratory	To determine if tumor-specific circulating DNA containing the c.395G>A (R132H) mutation can be detected in plasma before, during, and after study drug treatment.	Detection of tumor-specific circulating DNA containing R132H mutation. Mean changes in R132H mutation from baseline.	See Section 15.6		
Exploratory	To determine if 2-HG, a metabolite specifically produced by tumors with IDH R132H, can be detected in plasma by mass spectrometry before, during, and after study drug treatment.	Detection of 2-HG in plasma. Mean changes in 2-HG in plasma from baseline.	See Section 15.6		
Exploratory	To explore the impact of PEP _{IDH1M} vaccination on genetic alternations, differential protein expressions or post-translational modifications (PTMs) using quantitative proteomic strategies in patient-derived samples.	Changes between baseline and surgery in genetic alternations, differential protein expressions and post-translational modifications (PTMs)	See Section 15.6		

Table 1. Objectives and Endpoints

Exploratory	To demonstrate quantitative repeatable measures of metabolism change in IDH1+ gliomas via a standardized MRS protocol, patients will be scanned on the research MR scanner to establish same-day and longitudinal metabolite coefficient of variance and possible longitudinal metabolite changes.	Difference in levels of metabolism measured at same assessment. Changes from baseline in metabolism levels at each follow-up assessment.	See Section 15.6
-------------	---	---	------------------

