9.5 Single-Voxel MR Spectroscopy

To demonstrate quantitative repeatable measures of metabolism change in IDH1+ gliomas, patients will be scanned on the research MR scanner using standardized MRS protocol to assess same-day repeatability and to assess longitudinal metabolite changes.

The IDH1 mutation causes extreme overexpression of the onco-metabolite R-2-hydroxyglutarate (2HG) in all tumor cells. This can be non-invasively measured using clinical MRS methods. 2HG is a specific marker for IDH1 mutated gliomas because its concentration in 'wild' IDH1 gliomas is below the level of measurement of MRS.

Duke Radiology has a standard protocol for 2HG measures using a proven 2HG MEGA-LASER pulse sequence for Siemens MR scanners and [name] open source "Vespa" software for spectral simulation and fitting of the MEGA-LASER data. The protocol is available for immediate use on our research scanner as a part of the Duke Radiology's Center for Advanced MR Development (CAMRD).

We will assess subjects at up to 5 time points: baseline (after consent and before PEP_{IDH1M} vaccine #1), and up to 4 times prior to surgery. This will provide between 6-8 weeks of tumor/vaccine interaction. A typical 2HG protocol consists of 12-15 minutes of anatomical MRI and ~15-30 minutes of MRS data acquisition. An IDH1+ patient can usually be processed in a 1-2 hour time slot.

In order to establish same-day coefficients of variance and/or optimized acquisition parameters, patients may be scanned twice within a time point. Patients will be positioned and scanned in the MR scanner, then completely removed and put back into the scanner, and then positioned and scanned a second time. If necessary for patient comfort, this evolution can be done immediately or with a short rest period so long as scanning is finished within the booked period of time. Longitudinal acquisitions will also be analyzed for longitudinal metabolite coefficients of variance and possible longitudinal metabolite changes.

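### Section 15.6 checks same-day MRS repeatability only with a paired test of mean difference, which cannot show precision, and omits the coefficients of variance that Table 1 and Section 9.5 set as the aim

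*Combined protocol and SAP*

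**What the plan says.** The analysis is in the last numbered item of Section 15.6: "Paired comparison (e.g. paired t-tests) will be used to assess whether same-day measures on a patient are the same". The next sentence reads "Assuming repeatability, changes over time in levels of metabolism will be described". The section gives no alpha, agreement limit, margin or other criterion for repeatability, and does not mention a coefficient of variance.

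The aim is put differently elsewhere. In Table 1 (Section 8) patients are scanned "to establish same-day and longitudinal metabolite coefficient of variance and possible longitudinal metabolite changes". The matching endpoint is "Difference in levels of metabolism measured at same assessment", and the analysis column sends the reader to Section 15.6. Section 9.5 gives the purpose of the duplicate scans: "In order to establish same-day coefficients of variance and/or optimized acquisition parameters, patients may be scanned twice within a time point". It adds: "Longitudinal acquisitions will also be analyzed for longitudinal metabolite coefficients of variance and possible longitudinal metabolite changes". Duplicate scanning is therefore optional, and the number of scan-rescan pairs is not fixed. On scheduling, Section 9.5 says "We will assess subjects at up to 5 time points".

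**The concern.** Repeatability is a question about the size of the random error between two scans of the same patient on the same day. A paired t-test asks something else: whether the average difference between first and second scans is zero. Random error averages towards zero, so a non-significant result is compatible with any amount of scan noise. A precise method with a small consistent shift between first and second scan can, conversely, give a significant result.

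The objective is to demonstrate quantitative, repeatable metabolite measures. If the reported evidence is a paired test, the report cannot say how large a change must be before it stands out from scan noise. The descriptions of change over up to five time points would then lack that context. So would the further analyses in Section 15.6 that relate metabolic change to genomic expression, 2-HG and IDH expression.

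**Working it through.** The plan gives no alpha, power, sample size or precision limit for this analysis, so there is no stated figure to reproduce.

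**Inputs**
- Test: paired comparison, for example a paired t-test (Section 15.6).
- Alpha: not stated. Assumed 0.05 two-sided, with 0.10 as the alternative.
- Number of pairs, n: not stated, and duplicates are optional (Section 9.5). Section 15.4.2 allows up to 28 patients with a goal of 20 receiving at least 6 vaccines. Assumed one pair per patient, with n = 5, 10, 20 and 28.
- Within-subject CV of one scan: not stated. Assumed 2% to 100% of the mean.

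**Step 1. No systematic shift.** With differences d between the two scans, t = mean(d) / (SD(d) / √n). Multiplying every d by a constant leaves t unchanged, so scan noise cancels out. With normal errors the chance of non-significance is 1 − alpha at every CV and every n. Simulation (200,000 data sets per setting) agrees:

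| Setting | Non-significant |
|---|---|
| alpha 0.05, n = 5 to 28, CV 2% to 100% | 94.9% to 95.1% |
| alpha 0.10, same settings | about 90% |
| alpha 0.05, lognormal error (log SD 0.05 to 0.5), n = 10 and 20 | 95.3% to 96.1% |

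**Step 2. A fixed shift of 5% of the mean, n = 20, alpha 0.05.** The SD of a difference is √2 × CV × mean, so the noncentrality is 5 / (√2 × CV% / √20). At CV 5% this is 5 / (7.07 / 4.47) = 3.16; at CV 20% it is 5 / (28.28 / 4.47) = 0.79. The noncentral t distribution gives:

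| Scan CV | Non-significant |
|---|---|
| 2% | about 0% |
| 5% | 15% |
| 10% | 68% |
| 20% | 88% |
| 50% | 94% |

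The pass rate rises as precision worsens. Fewer pairs have the same effect: at CV 5% it is 15% with 20 pairs, 49% with 10 and 77% with 5. Repeating the 20-pair case with multiplicative error gives 17%, 69%, 88% and 94% at CV 5%, 10%, 20% and 50%.

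**Step 3. What a precision measure shows.** Repeatability coefficient = 1.96 × √2 × within-subject SD = 2.77 × SD. As a share of the mean this is 2.77 × 5 = 13.9% at CV 5%, 55% at CV 20% and 139% at CV 50%. Step 1 gives all three the same pass rate.

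**Step 4. How well n pairs estimate it.** The 95% limits for the within-subject SD are the estimate times √(n / χ²₀.₉₇₅,ₙ) and √(n / χ²₀.₀₂₅,ₙ):

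| Pairs | Lower factor | Upper factor |
|---|---|---|
| 5 | 0.62 | 2.45 |
| 10 | 0.70 | 1.75 |
| 20 | 0.77 | 1.44 |
| 28 | 0.79 | 1.35 |

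**The case against.** A reader might infer that the plan sets a rule under which p > 0.05 certifies the scans as repeatable, so that even a useless measure would be approved. The documents do not support that. Section 15.6 names no alpha, does not equate non-significance with repeatability, and does not say that the test result decides whether the longitudinal description goes ahead. Two consecutive sentences invite that reading, but it remains an inference.

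Nor does the plan disregard precision. Table 1 makes coefficients of variance part of the objective, and Section 9.5 commits to analysing the longitudinal ones. A team following the whole protocol would probably estimate them, and a very large CV would then be visible.

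The size of any practical harm is also unknown. The documents give no MRS precision, so nothing shows that 2HG changes would in fact be scan noise. The pass rates under a shift depend on assumptions, including the between-patient spread if the shift is proportional to the level.

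It may also be said that the test is only an example. That does not help: any paired test of zero location difference addresses shift rather than precision.

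What stands is narrower. The section that is meant to contain the analysis names a method that does not answer the objective, and omits the one that the rest of the protocol points to.

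**Conclusion.** The point holds as a mismatch between the aim in Table 1 and Section 9.5 and the analysis in Section 15.6. The named test is non-significant about 95% of the time at any scan CV when there is no shift, and it favours noisier measures when there is one. The 95% is simply 1 − alpha. It rests on an assumed two-sided alpha of 0.05 and no systematic shift; the number of pairs, also assumed, does not alter it.

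It would go too far to require that a patient's change be called real only when it exceeds the repeatability coefficient. Section 15.6 only describes changes, and with few optional pairs the coefficient is too uncertain for a hard threshold: at 5 pairs the SD limits run from 0.62 to 2.45 times the estimate.

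Severity is minor. The objective is exploratory, its longitudinal output is descriptive, and the primary safety endpoint, the ELISpot analysis, the sample size and the accrual suspension rules are untouched.

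**What to change.** Amend the metabolic imaging item in Section 15.6 as follows.
- Make the within-subject CV and the repeatability coefficient (1.96 × √2 × within-subject SD) from the duplicate scans the repeatability analysis, each with a 95% CI and the number of duplicate pairs.
- Keep the paired mean difference, with its CI, only as an estimate of scan-order bias.
- Carry over the longitudinal coefficient of variance that Section 9.5 already promises.
- Present longitudinal changes alongside the repeatability coefficient as context, not as a per-patient cut-off.
- A Bland-Altman plot is optional.

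The cost is SAP wording and minor analysis work, with no added scans, visits or patients. The limitation is precision. With 20 pairs the SD is known to within about 0.77 to 1.44 times its estimate, and much less well with 5, so the report should show the interval rather than the point estimate alone.
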